1.3.2. Retrospective Quantitative Imaging Analysis of PRM-151 Data

Imbio Lung Texture Analysis was applied retrospectively to HRCT obtained at screening and Day 57 in Study PRM151f-12GL. Limitations of retrospective analysis included, the fact that the datasets contained reconstructed images of variable slice thickness, reconstruction kernel and temporal correlation with the physiologic tests were available. In particular, the slice thicknesses for some CT scans were ≥ 5 mm for some subjects and volumetric HRCT was not available at both time points for any of the subjects. In addition, validation of the inspiratory volume was not prospectively controlled, with full inspiration of the subjects during the scan assumed but not specifically coached by the performing technologist or measured by spirometry. Lung Texture Analysis results were reported as change from screening to Day 57 in % total lung volume occupied by any of the ILA texture types (ground glass, reticular or honeycombing) and non-ILA (normal parenchyma or mild LAA). Areas of moderate or severe LAA that are characteristic of emphysema were excluded from the analysis. Quantitative imaging data was analyzed in 16 subjects who had ≤ 36 days between screening CT and Day 1 PFTs. There was a strong negative correlation between baseline FVC % predicted and percent of lung volume identified as ILA by Imbio Lung Texture Analysis software. Non-ILA lung decreased in all placebo subjects and was stable or increased in 5 PRM-151 treated subjects, all of whom had stable or increased FVC % predicted. There was no clear correlation between the magnitude of change in FVC% predicted and %Non-ILA, possibly due the limitations inherent to retrospective analysis of the HRCT data. The analysis was confounded in 4 subjects by apparent poor inspiratory effort and resultant

atelectasis and increase in overall lung density for the HRCT series that should have been performed at TLC on the Day 57.

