5.2.5.2 Secondary efficacy analyses

For all secondary efficacy endpoints, the analyses will be based on observed data only *i.e.*, no data will be imputed. All the following analyses will be performed on both the ATS and the PP analysis data set.

SO1: *To determine the effect size of PRM-151 relative to placebo in change from Baseline to Week 28 in normal lung parenchyma (normal + mild LAA) and interstitial lung abnormalities (ILA) as quantified on high-resolution CT (HRCT) imaging analysis, pooling subjects on a stable dose of pirfenidone or nintedanib with subjects not on other treatment for IPF.*

HRCT is performed at baseline and W28. Descriptive statistics will be computed by treatment group for baseline, week 28 and change from baseline to Week 28 in total lung volume and volume (in ml and % of total lung volume) of parenchyma features representative of normal lung (normal + mild LAA) and representative of interstitial lung abnormalities (ILA) as quantified by HRCT imaging (see section 8, Statistical table 14.2.6.1.1 and 14.2.6.2.2). A model similar to that of the primary analysis (see section 5.2.5.1) will be used to compare the two groups (Statistical tables 14.2.6.3.1 to 14.2.6.3.2, Figure 14.2.4.1 to 14.2.4.2). Individual's measurement of total lung volume and volume of parenchymal features quantified by HRCT imaging will be reported in Listing 16.2.6.3.

SO2: *To determine the effect size of PRM-151 relative to placebo in change from Baseline to Week 28 in mean FVC% predicted, separately in subjects on a stable dose of pirfenidone or nintedanib and in subjects not on other treatments for IPF.*

The same model as the one for the primary analysis (see section 5.2.5.1) will be used for each subgroup (Statistical table 14.2.7.1.1 to 14.2.7.2.2, Figure 14.2.5.1.1 to 14.2.5.2.2). All measurements of FVC [% predicted] will be reported in Listing 16.2.6.1.1.

SO3: *To determine the effect size of PRM-151 relative to placebo in change from Baseline to Week 28 in normal lung (defined as normal + mild LAA) parenchyma and interstitial lung abnormalities (ILA) as quantified on HRCT imaging analysis, separately in subjects on a stable dose of pirfenidone or nintedanib and in subjects not on other treatments for IPF.*

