5.2.5.3 Exploratory efficacy analyses

For all exploratory efficacy endpoints, the analyses will be based on observed data only *i.e.*, no data will be imputed.

EO1: To evaluate the efficacy and estimate the size of effect of PRM-151 relative to placebo in change from baseline to weeks 4, 8, 12, 16, 20, and 24 in FVC % predicted, FVC in ml and 6 minute walking distance, pooling subjects on a stable dose of pirfenidone or nintedanib with subjects not on other treatment for IPF and separately in subjects on a stable dose of pirfenidone or nintedanib and in subjects not on other treatments for IPF.

A model similar to that of the primary analysis (see section 5.2.5.1) but with the addition of random slopes will be used to evaluate on both the ATS and the PP data sets the efficacy and estimate, pooling subjects on a stable dose of pirfenidone or nintedanib with subjects not on other treatment for IPF and separately in subjects on a stable dose of pirfenidone or nintedanib and in subjects not on other treatments for IPF, the size of effect of PRM-151 relative to placebo in time variations in FVC [% predicted] (Statistical tables 14.2.13.1 to 14.2.14.2.2, Figures 14.2.10.1 to 14.2.11.2.2), FVC [ml] (Statistical tables 14.2.15.1 to 14.2.16.2.2, Figures 14.2.12.1 to 14.2.13.2.2) and 6MWD (Statistical tables 14.2.17.1 to 14.18.2.2, Figures 14.2.14.1 to 14.2.15.2.2). The individual slopes and intercepts will be listed (Listings 16.2.6.10 to 16.2.6.12). Statistical inference (90% CI and p-values) on the slope difference between treated and placebo groups will be reported.

EO2: To assess the impact of PRM-151 on disease related symptoms and quantitative imaging.

Mean change from Baseline to Week 28 in total lung volume and volume of parenchymal features (see section 8) on HRCT (in ml and % of total lung volume), representative of interstitial lung abnormalities (ILA) will be computed, comparing PRM151 vs. placebo (separately) in patients with SVC breathhold at CT scanning $\geq 90\%$ of SVC supine, with a similar approach to the one used

for the primary analysis (statistical tables 14.2.19.1.1.1 to 14.2.19.2.3.2, Figure 14.2.16.1.1 to 14.2.16.2.2).

For all categories of lung features (including PVV), the change from baseline to week 28 in volume of a given lung feature (both in ml as well as in % of total lung volume) will be computed in subjects treated with PRM-151 and placebo, depending on the completeness and usability of the obtained data.

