Change in Patient Reported Outcomes will be assessed based on the King's Brief Interstitial Lung Disease Questionnaire (K-BILD) and Leicester Cough Questionnaire (LCQ). Descriptive statistics for raw values and change from Baseline to each visit in total score of both questionnaire will be computed by treatment group. Differences between treatment groups in change from baseline to week 28 for total score of each questionnaire will be tested using a similar approach to the one used for the primary analysis (see section 5.2.5.1). These analysis will be performed on both the ATS and the PP data sets (Statistical tables 14.2.20.1.1 to 14.2.20.3.2 and 14.2.21.1.1 to 14.2.21.3.2, Figures 14.2.17.1 to 14.2.17.2 and 14.2.18.1 to 14.2.18.2). All results of K-BILD and LCQ will be reported in Listings 16.2.6.4.1 to 14.2.6.4.2.2 and 16.2.6.5.1 to 16.2.6.5.2.2.

For the LCQ, in addition to the above approach, frequency of patients with changes below or above 1.3 (identified as the minimal important difference) will be tabulated by treatment groups at week 4, 8, 12, 16, 20, 24 and 28 (Statistical table 14.2.21.4.1 and 14.2.21.4.2).

Descriptive statistics for raw values at each visit and change from baseline to each visit in anti-Pentraxin-2 antibodies measurements will be computed by treatment group. This analysis will be performed on both the ATS and the PP dataset (Statistical 14.2.22.1.1 to 14.2.22.2.2). Individual measurements of anti-pentraxin-2 antibodies will be reported in Listing 16.2.6.8.

EO3: To assess the use of quantitative imaging in IPF

The correlation between baseline FVC [% predicted], DLCO (corrected for Hb, [% predicted]), TLC by nitrogen washout, PROs and 6MWD and total lung volume and volume of parenchymal features on HRCT (in ml and % of total lung volume) representative of ILA by quantitative imaging, as well as change from Baseline to Week 28 in FVC [% predicted], DLCO (corrected for Hb, [% predicted]), TLC by nitrogen washout, PROs and 6MWD and change from Baseline to Week 28 in total lung volume and volume of parenchymal features on HRCT (in ml and % of total lung volume) representative of ILA will be computed. This analysis will be performed on both the ATS and the PP dataset (Statistical tables 14.2.23.1.1 to 14.2.23.1.2).

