For all categories of lung features (including PVV) the correlation between (i) change from baseline to week 28 in volume of a given lung feature (both in ml as well as in % of total lung volume) and (ii) change from baseline to week 28 in FVC [% predicted] will be computed. This analysis will be performed on both the ATS and the PP dataset (Statistical tables 14.2.23.2.1 to 14.2.23.2.2).

For all categories of lung features (including PVV) the correlation between (i) change from baseline to week 28 in volume of a given lung feature (both in ml as well as in % of total lung volume) and (ii) change from baseline to week 28 in DLCO will be computed. This analysis will be performed on both the ATS and the PP datasets (Statistical table 14.2.23.3.1 to 14.2.23.3.2).

The impact of inspiratory effort on results of HRCT quantitative imaging will be assessed by (Statistical table 14.2.23.4.1 to 14.2.23.4.2, Figure 14.2.19.1 to 14.2.19.2):

1. Calculating the proportion of patients performing spirometry guided HRCT with a SVC breathhold at CT scanning $\geq 90\%$ of SVC supine at baseline and at week 28
2. The correlation of SVC breathhold at CT scanning and SVC supine at baseline and at week 28
3. The correlation between (i) baseline Total lung volume by quantitative imaging and (ii) baseline TLC by nitrogen washout, separately for patients with SVC breathhold at CT scanning $\geq 90\%$ of SVC supine, and for patients with SVC $< 90\%$ or not receiving spirometry-guided HRCT.

EO4: To assess the impact of PRM-151, disease pathogenesis and disease progression on exploratory serum, cellular and genetic biomarkers

To assess the impact of PRM-151 on exploratory biomarkers, descriptive statistics for change from baseline to week 28 in biomarkers will be computed by treatment group and by baseline genetic status (MUC5B and TLR polymorphism separately). These analyses will be performed on both the ATS and the PP dataset (Statistical table 14.2.24.1 and 14.2.24.2). Individual biomarker values will be reported in Listing 16.2.6.6. All or part of these analyses may be provided at a later stage than the rest of the analyses described in the SAP, might the corresponding data not be available at the time of the database lock. It is currently anticipated that baseline genetic status will be available, but biomarkers will not.

Additional exploratory analysis: ADA vs. FVC [% predicted]

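### For patients scanned without spirometry guidance, no planned statistic measures how far CT lung volume departs from nitrogen-washout TLC at Baseline or Week 28

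*SAP*

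**What the plan says.** SAP 5.2.5.3, under EO3, lists three ways of assessing what inspiratory effort does to the HRCT results (tables 14.2.23.4.1 to 14.2.23.4.2):

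- Item 1 is a threshold measure at baseline and Week 28: "Calculating the proportion of patients performing spirometry guided HRCT with a SVC breathhold at CT scanning" of at least 90% of supine SVC.
- Item 2 is "The correlation of SVC breathhold at CT scanning and SVC supine at baseline and at week 28".
- Item 3 is "The correlation between (i) baseline Total lung volume by quantitative imaging and (ii) baseline TLC by nitrogen washout". It is computed separately for patients at or above 90% and for a second group that joins those below 90% to those "or not receiving spirometry-guided HRCT".

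Other parts of the SAP touch the same question:

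- The first paragraph of EO3 correlates changes as well as baseline values; the variables include "TLC by nitrogen washout, PROs and 6MWD and change from Baseline to Week 28 in total lung volume". It is not split by breath-hold quality.
- EO2 compares the arms on HRCT change "in patients with SVC breathhold at CT scanning" at or above the 90% mark. The list of tables (9.1) adds a matching set for patients below it.
- SO1 in 5.2.5.2 gives descriptive statistics by arm for baseline, Week 28 and "change from baseline to Week 28 in total lung volume and volume" of the parenchymal features.

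On the data side, protocol 7.10.3 has spirometry during CT at selected sites, without saying how many sites or patients. Protocol 7.10.1 has washout TLC at Screening, Baseline and Week 28. SAP section 8 defines CT total lung volume without vessels.

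**The concern.** A scan taken short of full inspiration shows a smaller and denser lung. Protocol 1.3.2 reports this from the previous study: "The analysis was confounded in 4 subjects by apparent poor inspiratory effort", at the Day 57 follow-up scan, in an analysis of 16 subjects. The secondary HRCT endpoints here are changes from Baseline to Week 28, so the threat is effort that differs between the two visits. If the change in effort also differs between arms, the treatment comparison is biased; if it does not, the comparison is noisier and the mean change in each arm is hard to read.

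Guided patients have a direct measure of effort at both visits. Unguided patients do not. For them the only yardstick is washout TLC, and the SAP uses it only through correlations. Correlation across patients mainly reflects that large lungs are large by both methods. It does not say whether the two volumes agree, or whether their relation moved between visits. Item 3 looks at baseline alone and mixes unguided patients with known failures, so it cannot describe the unguided group.

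**Working it through.** The documents give no figure to reproduce on this point. The lung volumes and error sizes below are assumptions chosen to show how the planned statistics behave.

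**1. Item 3 under a mean shortfall.** Write CT volume = R × TLC, with R independent of TLC, mean m and SD s; TLC has mean μ and SD σ. Then

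r = m / √(m² + s²(1 + μ²/σ²)).

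Assume μ = 4.5 L and σ = 1 L, so 1 + μ²/σ² = 21.25.

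| Mean ratio m | Mean shortfall | r, s = 0.05 | r, s = 0.10 |
|---|---|---|---|
| 1.00 | 0 | 1/√1.0531 = 0.974 | 1/√1.2125 = 0.908 |
| 0.85 | 0.15 × 4.5 = 0.68 L | 0.85/√0.7756 = 0.965 | 0.85/√0.9350 = 0.879 |
| 0.75 | 0.25 × 4.5 = 1.1 L | 0.75/√0.6156 = 0.956 | 0.75/√0.7750 = 0.852 |

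The unknown s moves r more than a shortfall of over a litre does. If the error scales with the volume inspired, CT = f × TLC × (1 + e), then f cancels and r does not change at all.

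**2. What item 1 does in guided patients.** Simulation of 400,000 draws, assumed supine SVC 2.8 L (SD 0.7), 5% proportional noise, breath-hold = f × full inspiration:

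| f | Correlation (item 2) | Proportion at or above 90% (item 1) |
|---|---|---|
| 1.00 | 0.979 | 97.7% |
| 0.90 | 0.979 | 50.1% |
| 0.85 | 0.979 | 12.0% |
| 0.80 | 0.979 | 0.6% |

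At f = 0.80 the proportion is 0% with 3% noise and 5.9% with 8% noise. Item 2 is blind to the shortfall; item 1 is not.

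**3. Unguided patients, effort falling at Week 28 only.** Assumed TLC 4.2 L (SD 0.9), true change −0.1 L (SD 0.25), 5% noise, common 20% shortfall at Week 28:

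- Item 3 is unaffected, because it stops at baseline (r = 0.973). Even the same correlation at Week 28 would be 0.976, with or without the shortfall.
- The EO3 correlation of changes goes from 0.64 to 0.52. Noise alone moves it further: with no shortfall it is 0.81 at 3% noise and 0.46 at 8%. It therefore cannot be interpreted without a reference value.
- The mean CT change is 0.8 × (4.2 − 0.1) − 4.2 = −0.92 L, against −0.10 L by washout. This contrast shows the problem at once, but no described output places the two figures together. No title in the SAP's lists of tables, figures or listings names washout TLC.

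**4. Pooling in item 3.** Same TLC and noise, failed holds at f = 0.75 mixed with full unguided holds. Each part alone has r of about 0.973. With 10%, 25% and 50% failed holds the pooled r is 0.916, 0.858 and 0.810. The pooled value describes neither part and depends on the mix, which the documents do not give.

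**The case against.** A reader might infer that the SAP judges effort by correlation alone and that a large systematic shortfall would go unseen anywhere in the trial. The documents do not support that. Item 1 is a threshold proportion at both visits and would expose such a shortfall in guided patients. EO2, with the table list, gives separate HRCT analyses at or above and below 90%. EO3 also correlates changes to Week 28, so the baseline restriction belongs to item 3 and not to the whole SAP. SO1 would show a fall in CT volume by arm. No acceptance rule depends on any value of r, so nothing commits the sponsor to reading a high correlation as adequate inspiration.

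The sizes above also rest on assumed lung volumes and a uniform shortfall. The one precedent was patchy, in a study where inspiration was neither coached nor measured, and patchy failure does lower a correlation.

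These points stand, and they confine the concern to unguided patients. They do not remove it there. Item 1 and the EO2 split need a guided breath-hold. The change correlation lacks a reference value, and the tables cited for it carry a title that mentions baseline correlations only. A fall in CT volume without washout TLC beside it cannot be separated from disease progression. A drop in item 3 could come from the known failures in its pooled group.

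It would also be wrong to conclude that the correlations should be dropped. SAP 4.1.3 names the correlation of washout and imaging volumes as an exploratory endpoint.

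**Conclusion.** The concern holds in a limited form. For patients scanned without spirometry guidance, no planned statistic measures the difference between CT total lung volume and washout TLC at either visit. The effort check that covers them in the EO3 list is a baseline-only correlation, which would stay near 0.96 under a 15% to 25% mean shortfall (ratio SD 5%, TLC 4.5 L, SD 1 L) and is pooled with known failed breath-holds.

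That correlation is nearly insensitive to a common proportional shortfall follows from the algebra. The particular values depend on the assumptions. How many patients are affected is unknown, because the number of guided sites is not stated.

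Severity is low. These are exploratory, descriptive outputs; they matter for reading the secondary HRCT endpoints and have no bearing on the primary FVC analysis.

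**What to change.** Keep items 1 to 3 and add to table 14.2.23.4:

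- The ratio (or difference) of CT total lung volume to washout TLC at Baseline and at Week 28, with mean, limits of agreement and within-patient change, by arm.
- Three groups in place of two: at least 90%, below 90%, and not guided. State which visit's breath-hold assigns a patient to a group.
- For guided patients, the ratio of breath-hold SVC to supine SVC at both visits. This also shows movement above the threshold, such as 100% to 91%, which item 1 counts as a pass both times. It cannot be computed for unguided patients.

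Because CT volume excludes vessels, some offset from TLC is expected even at full inspiration. The within-patient change in the ratio is the informative figure.

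The cost is a revised table shell and a little more programming, on data already collected at both visits. With about 117 patients randomised 2:1 (78 and 39) and an unstated number of guided sites, some cells will be small and their limits of agreement wide. They should be read as descriptive.

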7.9.1. Prohibited Concurrent Medications

The following medications are prohibited during the study:

- All investigational therapies other than PRM-151 for any indication, including therapies that are approved in other indications that are being investigated in IPF, are prohibited within 4 weeks before Screening and during study participation.
- Inhaled or systemic corticosteroids. (Low dose [≤ 10 mg daily] corticosteroids are permissible, provided the dose has been stable for 30 days prior to Baseline.)
- Bronchodilators:
 - Short-acting bronchodilator use within 12 hours of pulmonary function, DLco, and 6MWT assessments.
 - Long acting bronchodilators are disallowed the day of and within 24 hours of pulmonary function testing, DLco, and 6MWT assessments.
- The use of inhaled bronchodilator agents at times outside these windows is permissible.
- Immuno-suppressants (e.g. methotrexate, azathioprine, cyclophosphamide, cyclosporine, everolimus or other immunosuppressants including those used after organ transplant) are prohibited within 4 weeks of baseline and during the study.

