8.3. Protocol deviations

Major protocol deviations are defined as deviations liable to prevent or change the interpretation of the results of the primary efficacy analysis of the study. The following deviations will be considered as major (this list is not exhaustive and will be reviewed at the time of the blind review meeting):

- noncompliance with the inclusion or non-inclusion criteria
- noncompliance with study treatment
- no post-baseline data for the primary efficacy endpoint
- intake of forbidden medication

All other deviations will be considered as minor deviations. However, all deviations will be reviewed and adjudicated as either major or minor during the blind review meeting before database lock and code break.

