3.3 Per-protocol (PP) dataset

The Per Protocol (PP) set will comprise of a subset of the ATS analysis population:

- Randomized
- treated with the IMP,
- having received the planned IMP infusions at least for the complete three first cycles
- who did not present any major protocol deviations.
- who have at least one post-cycle 3 evaluation of the primary efficacy criterion (FVC [% predicted])

The PP dataset will be used for secondary analyses of the primary efficacy criterion and for the analysis of some selected secondary efficacy criteria, as described in section 5.2.5.2.

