4.1.3 Exploratory efficacy endpoints

There are five types of exploratory endpoints for the study.

The first type is based on the examination of FVC [% predicted, and ml] and 6MWT [m]:

- Change from Baseline at Weeks 4, 8, 12, 16, 20, 24 and 28 for the FVC [% predicted], FVC [ml], and 6MWT distance [m].
- Change in FVC for patient subsets on either a stable dose of (i) pirfenidone or (ii) on a stable dose of nintedanib.

The second type of exploratory endpoints is based on structural imaging:

- Transitions from Baseline to Week 28 between all categories of lung features (normal, ground glass density, reticular changes, honeycombing, and mild, moderate, and severe low attenuation areas) by quantitative imaging software, will be analyzed upon further development of methodology to measure transitions.
- Correlation of transitions between categories of lung features by quantitative imaging and changes in FVC [% predicted], will be analyzed upon further development of methodology to measure transitions.
- Correlation of transitions between categories of lung features by quantitative imaging and changes in DLCO, will be analyzed upon further development of methodology to measure transitions.
- Correlation between total lung volume by nitrogen washout and total lung volume by imaging
- Correlation of changes in interstitial lung abnormalities and PROs and 6MWD
- Impact of inspiratory effort on results of HRCT quantitative imaging.
- Pulmonary Vessel Volume.
- Mean change from Baseline to Week 28 in total lung volume and volume of parenchymal features on HRCT (in ml and % of total lung volume), representative of interstitial lung abnormalities (ILA) in patients with SVC breathhold at CT scanning $\geq 90\%$ of SVC supine (comparing PRM151 vs placebo)

The third group of exploratory endpoint is based on patient reported outcomes:

- Change in Patient Reported Outcomes as measured by
 - King's Brief Interstitial Lung Disease Questionnaire (K-BILD) and
 - Leicester Cough Questionnaire (LCQ) from Baseline to Week 28.

The fourth group of exploratory endpoint is based project investigator assessed outcome :

- Acute exacerbations and time to first reported acute exacerbation

The fifth group of exploratory endpoints is related to the analysis of biomarkers:

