The relationship between Anti-Pentraxin 2 antibodies (ADA) presence and level of FVC [% predicted] in time will be studied by modelling the influence of presence/absence (and/or level) of ADA in the repeated measures mixed model used for the primary efficacy analysis (see section 5.2.5.1) and if relevant using non-parametric spline functions. The most parsimonious model will be chosen on the basis of the AIC (Statistical table 14.2.25.1 and 14.2.25.2).

Additional exploratory analysis: Baseline characteristics vs. FVC

If data lend themselves to it, additional exploratory analysis will be done to test for interaction between baseline characteristics (e.g., FVC/DLCO/6MWD) and change in FVC.

Exploratory analysis of PK/PD relationship

Descriptive statistics and correlation will be computed to explore the relationship of Pentraxin-2 levels vs FVC [% predicted]/FVC [ml]/slope of FVC ml at week 24 and 28, and the relationship of

Pentraxin-2 vs other PFTs/PROs/6MWT (Statistical table 14.2.26.1 and 14.2.26.2). If relevant the corresponding scatter plot will be produced.

Exploratory analysis of relationship between Pentraxin-2 levels and ADA

Correlation coefficient between Pentraxin-2 levels and ADA titer at week 28 will be computed (Statistical tables 14.2.27.1 and 14.2.27.2) and a scatterplot prepared (using logarithmic coordinates for titers).

Exploratory analysis of acute exacerbations

Tabulation of each type of acute exacerbations will be produced (Statistical table 14.2.28.1.1 and 14.2.28.1.2). Descriptive statistic and Kaplan-meier curve will be computed by treatment group for time to first reported acute exacerbation (Statistical tables 14.2.28.2.1 and 14.2.28.2.2).

Additional exploratory analysis: FVC [% predicted] separately on pirfenidone and nintedanib

The same model as the one for the primary analysis (see section 5.2.5.1) will be used separately on (i) patient on a stable dose pirfenidone and (ii) patient on a stable dose of nintedanib (Statistical table 14.2.20.1.1 to 14.2.20.2.2).

Additional exploratory analysis: time variation in historic FVC [% predicted; ml] measurements:

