6.3 Changes in exploratory efficacy analyses

All exploratory efficacy analysis will be performed on both the ATS and the PP.

It was initially planned (EO1) to evaluate the efficacy and estimate the size of effect of PRM-151 relative to placebo in change from baseline to weeks 4, 8, 12, 16, 20, and 24 in FVC % predicted, FVC in ml and 6 minute walking distance using mixed models with random intercepts. To obtain a better description of individual variability, both random intercepts and random slopes will be used.

The following not initially planned exploratory analysis were added (see section 5.2.5.3 for details):

- To assess the use of quantitative imaging in IPF (E03)
- To explore the relationship between Anti-Pentraxin 2 antibodies (ADA) presence and level of FVC [% predicted] in time
- To explore PK/PD relationship.
- To explore relationship between Pentraxin-2 levels and ADA
- To explore acute exacerbations
- To explore time variations in FVC % predicted separately in patient (i) on stable dose of pirfenidone and (ii) on a stable dose of pirfenidone.

7 Software documentation

All summaries and statistical analyses will be generated using SAS version 9.4 or higher.

8 Derived data

Derived variable	Derivation algorithm
Change from baseline to visit V (continuous)	Change from baseline of variable $X = X_{(Visit V)} - X_{(Baseline)}$ 
 ○ Negative values indicate a decrease in X ○ Positive values indicate an increase in X

Percent change from baseline to visit V (continuous)	Percent change from baseline of variable X= $100 * [X_{(Visit V)} - X_{(Baseline)}] / X_{(Baseline)}$ 
 ○ Negative values indicate a decrease in X ○ Positive values indicate an increase in X
Treatment compliance	Continuous variable: The compliance C_i for patient i will be computed according to: $C_i = \frac{D_i^t * 100}{D_i^p}$ 
where D_i^p mg is the total amount (mg) of IP prescribed to patient i and D_i^t is the total amount (mg) of IP actually taken by the patient during the study i.e., before the end of study for patient i.

Treatment compliance (categorical)	Categorical variable with three modalities: 
 • $C_i < 80\%$ • $80\% \leq C_i < 120\%$ • $C_i \geq 120\%$

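### The per-protocol version of time to first acute exacerbation runs from baseline, although entry to that set requires treatment through Week 8 and a later FVC, so some early events remove the patient being counted

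*SAP*

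**What the plan says.** SAP 4.1.3 lists among the exploratory efficacy endpoints: "Acute exacerbations and time to first reported acute exacerbation". For these, SAP 5.2.5.3 plans a tabulation by type, and then: "Descriptive statistic and Kaplan-meier curve will be computed by treatment group for time to first reported acute exacerbation". It specifies no test and no time origin other than the usual one.

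That paragraph does not name the analysis sets, but SAP 6.3 does: "All exploratory efficacy analysis will be performed on both the ATS and the PP". The table numbers agree. The tabulation has tables 14.2.28.1.1 and 14.2.28.1.2, and time to event has 14.2.28.2.1 and 14.2.28.2.2. SAP 5.2.5.3 uses the same pairing expressly for ATS and PP in the biomarker tables 14.2.24.1 and 14.2.24.2.

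The ATS (SAP 3.2) asks only for randomization and one administration. The PP set (SAP 3.3) adds three conditions: "having received the planned IMP infusions at least for the complete three first cycles"; no major deviation; and, for the last, patients "who have at least one post-cycle 3 evaluation of the primary efficacy criterion".

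**The concern.** The PP conditions are met or failed after baseline, and an acute exacerbation can decide which. A curve that starts at baseline but is drawn only for patients who later qualified has lost some of its early events by construction. The event being analysed helps to determine who is analysed.

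Two things are at stake. A reader who sets the PP curve beside the ATS curve could take a lower early risk for a feature of protocol-compliant treatment. And if PRM-151 changes how often an exacerbation ends treatment, the PP contrast between arms moves even when the drug has no effect on exacerbations.

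**Working it through.** The plan gives no exacerbation rate or event count, so there is no figure of its own to reproduce. The sample size of 102 evaluable subjects concerns FVC and does not bear on this point.

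**1. When the PP conditions bite.** SAP 5.2.2 places cycle 7 at Week 24. With four-weekly cycles, cycle k falls at Week 4 × (k − 1), so cycle 3 is at Week 4 × 2 = 8. Protocol 6.2 and 7.10 put assessments before dosing, so the Week 8 FVC precedes the cycle 3 infusion. The first scheduled FVC after cycle 3 is at Week 12. (Protocol 8.4 words the PP set differently and requires the Week 12 infusion; the SAP definition is used here.)

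**2. Who is removed.** Adverse event and disease progression are both listed reasons for stopping treatment (SAP 3.1.3).

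| Course of an early exacerbation | PP set, absent another major deviation |
|---|---|
| Treatment ends before the Week 8 infusion | Out |
| Week 8 infusion given, then death or no further FVC | Out |
| Treatment continues, FVC at Week 12 or later | In, event counted |
| Treatment stops after Week 8, End of Study FVC done | Can be in |

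The last row follows from Protocol 5.4 (End of Study visit four weeks after the last dose) and SAP 5.4.4 (its data are reallocated to the visit following the last infusion, here Week 12).

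**3. Share of patients with an exacerbation who are lost.** Assumptions, not in the documents: first events are spread evenly over 28 weeks, and a fraction q of those before the cut-off leads to exclusion, with q from 25% to 75%. Share lost = (cut-off / 28) × q.

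- Week 8: 8/28 = 0.286; × 0.25 = 0.07; × 0.75 = 0.21.
- Week 12: 12/28 = 0.429; × 0.25 = 0.11; × 0.75 = 0.32.

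The Week 12 line is an upper bound, because between Weeks 8 and 12 only death or a missing FVC removes a patient.

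**4. Effect on the estimated risk.** Further assumptions: constant hazard, Week 28 risk P, and no other exclusions. With E the risk before the cut-off, E = 1 − (1 − P)^(cut-off/28), and PP risk = (P − qE) / (1 − qE). For P = 10%, Week 12 and q = 50%: E = 0.0442, qE = 0.0221, and PP risk = 0.0779 / 0.9779 = 8.0%.

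| P = 10% | q = 25% | q = 50% | q = 75% |
|---|---|---|---|
| Week 8 | 9.3% | 8.6% | 8.0% |
| Week 12 | 9.0% | 8.0% | 6.9% |

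Over P = 5% to 20%, the relative fall is 6-21% with the Week 8 cut-off and 9-32% with Week 12. Of 117 patients, this is about 0.4 to 8 removed.

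**5. Effect on the comparison, with no true effect.** Equal q in both arms leaves the risk ratio (PRM-151 over placebo) at 1.00. For P = 10% to 20%, q = 75% on PRM-151 and 25% on placebo gives 0.77 to 0.86; the reverse gives 1.16 to 1.30.

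**The case against.** The strongest reply is that nothing rests on this output. It is exploratory and has no test. The unfiltered ATS version is already planned. Respiratory decline events and deaths are tabulated on the SAF (SAP 5.2.6.1 and 5.2.6.2). SAP 5.3.5 draws efficacy conclusions from the single primary analysis. All of this stands, and it sets the severity.

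Other replies stop readers from inferring more than the documents support:

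- **A fully protected window of 12 weeks.** Not supported. The last required infusion is at Week 8, and a patient who stops after it can qualify through the End of Study FVC. Patients who exacerbate early and continue also stay in.
- **Treatment of an exacerbation removes the patient at any week.** Protocol 7.9.1 prohibits "Inhaled or systemic corticosteroids" apart from a stable low dose, and Protocol 8.3 lists "intake of forbidden medication" as a major deviation, so this route is possible. But every deviation is adjudicated at blind review, and SAP 3.1.1 refers to a separate deviation guidance document that is not available here. Whether the route operates cannot be settled from the two documents.
- **A low bias in both arms as a certainty.** The PP set also drops patients who never had an exacerbation. The risk falls only if patients with one are excluded more often than the rest, which is likely but not shown.
- **False reassurance from agreement of the PP and ATS results on FVC.** That would need the medication route to operate, so it does not follow.

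**Conclusion.** The point holds in limited form. The PP exacerbation outputs run from baseline on a set whose membership an early exacerbation can revoke, and the SAP has neither a later starting point nor a label to say so. The PP event risk is likely understated. The contrast between arms is distorted only if event-driven exclusions differ by arm.

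The figures are illustrations that rest on evenly spread events (or a constant hazard) and on an assumed 25-75% of early events leading to exclusion. The Week 8 range of 7-21% is the better guide to size, and 32% is a ceiling. Severity is minor: no stated conclusion of the trial depends on these tables.

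**What to change.** In SAP 5.2.5.3 and 6.3, state that the acute-exacerbation tabulation and time to first exacerbation are run on the ATS (or SAF) only, and delete tables 14.2.28.1.2 and 14.2.28.2.2.

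If a PP version is wanted, start each patient's clock at the qualifying post-cycle-3 FVC visit, count only first events after it, and title the output as conditional on completing three cycles.

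At blind review, also confirm that medication given for a respiratory decline event does not by itself exclude a patient from the PP set, and check this against the deviation guidance document. This concerns analysis-set membership only; no treatment rule is proposed.

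The cost is a few SAP sentences and two fewer tables, with no new data. The downside is that this exploratory endpoint then has no PP version that runs from baseline.
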